## 8. Benefits

No direct benefit is anticipated. Participants may improve their ability to cope with pain and improve their mood, pain, and disability. Information gained through this study may lead to a better understanding the importance of delivery method of mind body interventions. The potential benefits from this study far outweigh the potential risks. The data collected as part of this study may ultimately

help researchers and clinicians develop novel digital therapeutics to better care for patients with acute injuries to prevent chronic pain and disability.

## 9. Statistical Analysis

We will not test for efficacy of the VR program, in line with guidelines for feasibility studies and the NIH Stage Model and NCCIH framework. Instead, we will calculate frequency and proportions to assess feasibility Go/No-go benchmarks consistent with virtual pilot studies of mind-body interventions (see table below). Power analysis is not appropriate for small feasibility pilot studies. The sample size of 10 is appropriate for early feasibility testing and achieving thematic saturation in the exit interviews. Participants who drop-out will be counted as not meeting applicable feasibility criteria. If these benchmarks are not met, revisions will be necessary prior to an efficacy trial. Exploratory analyses: I will calculate paired t-tests, effect sizes of improvement, and exploratory correlations for each quantitative measure.

Feasibility markers	Acceptable	Excellent
Credibility and Expectancy	>70% score over scale midpoint	≥ 80% score over scale midpoint
Client Satisfaction Score	> 70% score over scale midpoint	≥ 80% score over scale midpoint
Feasibility of recruitment	> 70% approached participate	≥ 80% of approached participate
Acceptability of treatment	> 70% attend 6 out of 8 weeks	≥ 80% attend 6 out of 8 weeks
Adherence to pain survey	> 70% of biweekly surveys	≥ 80% of biweekly surveys
Feasibility of assessments	> 70% have no measures missing	≥ 80% have no measures missing
System Usability	> 70% score over scale midpoint	≥ 80% score over scale midpoint
Motion Sickness/Nausea	> 70% score below scale midpoint	≥ 80% score below scale midpoint
Other Adverse Events	Minimal	None

We will analyze qualitative data from the exit interviews using NVIVO 12 using the framework method and a hybrid inductive-deductive approach. This will include predetermined themes while allowing for inductive flexibility where themes and codes are induced by data to allow for novel ideas to optimize the VR program. We will code the raw qualitative data and the RA will perform reliability coding. The PI resolve discrepancies with the RA to achieve sufficient reliability ( $\kappa > .80$ ). We will use the qualitative feedback to improve the study procedures for subsequent trials.

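### The primary Go/No-Go benchmarks are read from bare proportions in ten participants with no interval, although a pass at 8/10 or 9/10 does not show a true rate above 70%

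*Combined protocol and SAP*

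**What the plan says.** Section 3 (General Description of Study Design) makes the Go/No-Go feasibility markers the primary outcome of this single-arm pilot. Section 9 gives their entire quantitative analysis: "we will calculate frequency and proportions to assess feasibility Go/No-go benchmarks consistent with virtual pilot studies of mind-body interventions".

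The table in Section 9 has two tiers. For treatment acceptability, for example, the acceptable tier is "> 70% attend 6 out of 8 weeks" and the excellent tier is "≥ 80% attend 6 out of 8 weeks".

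On size, Section 9 says "The sample size of 10 is appropriate for early feasibility testing and achieving thematic saturation in the exit interviews" and "Power analysis is not appropriate for small feasibility pilot studies". Drop-outs are scored as failing whichever criteria apply to them. One consequence is written down: "If these benchmarks are not met, revisions will be necessary prior to an efficacy trial". Neither a confidence interval nor a statement of precision appears anywhere in the document.

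**The concern.** The benchmarks are compared with 70% and 80% as though the observed proportion were the true one. In ten people the sampling error is large relative to the gap between an adequate and an inadequate rate. A row reported as 80% and excellent could come from a program whose true rate is well below 70%, and a sound program could miss by chance. The results decide whether revisions come before an efficacy trial, and Section 3 lists preliminary feasibility and a subsequent NIH proposal among the deliverables. A reader of those results would have nothing in the planned output to show how little ten observations pin down.

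**Working it through.** **Inputs from the documents.** N = 10 (Sections 3 and 9); acceptable means more than 70% and excellent means at least 80% (Section 9 table); drop-outs count as failures, so the denominator stays at 10. N = 10 is stated and not derived, so there is no calculation of the plan's to reproduce.

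**Assumption.** The documents give no confidence level, sidedness or interval method. I use 95% and the two-sided exact interval, and show alternatives where they matter.

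**Rows covered.** Six rows are counted over participants: credibility/expectancy, satisfaction, treatment acceptability, completeness of assessments, usability, and motion sickness/nausea. Recruitment ("> 70% approached participate") is counted over people approached, survey adherence appears to be counted over surveys, and other adverse events has no proportion. The figures below do not apply to those three.

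**Count needed.** 7/10 is exactly 70% and does not exceed it, so a pass needs x ≥ 8. Since 8/10 = 80%, the acceptable and excellent tiers require the same count at N = 10.

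**Interval.** Clopper-Pearson two-sided 95%: lower limit = Beta quantile(0.025; x, n − x + 1); upper limit = Beta quantile(0.975; x + 1, n − x).

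| Result | Exact two-sided 95% CI | Range of lower limits over methods tried* |
|---|---|---|
| 8/10 | 44.4% to 97.5% | 44.4% to 49.7% |
| 9/10 | 55.5% to 99.7% | 55.5% to 61.9% |
| 10/10 | 69.2% to 100% | 67.9% to 78.3% |

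*Two-sided Clopper-Pearson, one-sided 95% exact, Wilson, Agresti-Coull, Jeffreys.

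For 8/10 and 9/10 every method leaves the lower limit below 70%. For 10/10 the answer depends on the method:

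- Two-sided Clopper-Pearson: 0.025^(1/10) = 69.2%, short of 70% by 0.8 points.
- Agresti-Coull: 67.9%.
- One-sided 95% exact: 0.05^(1/10) = 74.1%.
- Wilson: 72.2%.
- Jeffreys: 78.3%.
- Exact binomial test of 10/10 against 70%: one-sided p = 0.7^10 = 0.028; two-sided p = 0.039.

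**Chance of passing one row.** P(X ≥ 8) = 45p^8(1 − p)^2 + 10p^9(1 − p) + p^10.

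- p = 0.60: 0.1209 + 0.0403 + 0.0060 = 0.167.
- p = 0.70: 0.2335 + 0.1211 + 0.0282 = 0.383.
- p = 0.80: 0.3020 + 0.2684 + 0.1074 = 0.678, so the row is missed with probability 0.322.

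**The case against.** The best defence is that this is an early feasibility pilot that declines a power analysis, disclaims efficacy testing and uses exit interviews to improve procedures. Nowhere does it say that a met benchmark proves a true rate above 70%. The only written consequence is for benchmarks not met; that a pass means go is implied by the label alone. This stands, and it limits the point to how the results are reported and interpreted. It does not justify omitting intervals. Precision is a separate matter from power, and a rule on whether to revise before the next trial uses the observed rate as a guide to future participants. The interviews do not quantify uncertainty in the proportions.

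It is also fair to say that intervals leave the pass and miss probabilities untouched, because those follow from N = 10 and the cut-off. That stands too. The intervals change only what may be concluded from a pass or a miss.

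Four stronger readings are tempting, and the documents do not support them:

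- A reader might infer that no result in ten people can exclude 70%. Low results do: 3/10 has an exact 95% interval of 6.7% to 65.2%, so a clear failure is detectable.
- A reader might infer that even 10/10 falls short. That holds for two-sided Clopper-Pearson and Agresti-Coull but not for the one-sided exact limit, which suits a one-directional benchmark, nor for Wilson or Jeffreys. The plan names no method.
- A reader might multiply the single-row pass probabilities to get the chance of meeting all six. That needs independence, which is implausible: the same ten people supply every row, and one drop-out fails every applicable row together.
- A reader might infer that the lower limits should become the next trial's planning values. The documents do not say these rates will set planning assumptions, and a lower limit of 44.4% after 8/10 is not an obvious planning value.

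**Conclusion.** The point holds as a cheap improvement. The primary outcome is assessed from proportions in ten participants with no planned measure of uncertainty, and two of the three possible passing results, 8/10 and 9/10, do not show a true rate above 70% by any interval tried. At the minimum pass, true rates from 44.4% to 97.5% are compatible with the data. A true rate of exactly 70%, which does not exceed the benchmark, still passes a row 38.3% of the time. Only 10/10 is borderline.

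This rests on a 95% level, a denominator of ten on the six participant-level rows, and the single-row binomial model. It does not make the pilot invalid, and it does not rest on any claim by the plan to have established a population rate.

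**What to change.** In Section 9, change the description of the benchmark analysis to: frequencies, proportions and exact (Clopper-Pearson) 95% confidence intervals for each participant-level row. Add one sentence: a benchmark that is met describes the observed proportion in this sample and does not establish that the true rate exceeds 70%.

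Sample size and thresholds stay as they are. The cost is two edits to Section 9, one more column in the results table, and a stated conclusion that is less favourable than a bare 80% would suggest.

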#### **4b. Local Recruitment Procedures**

We will recruit patients with acute orthopedic musculoskeletal injuries who are at risk for chronic pain and disability (PCS  $\geq$  20 and PASS-20  $\geq$  40) and meet inclusionary/exclusionary criteria. With a trained RA, we will recruit patients from the MGB Orthopedics Departments through established partnerships on active trials (~220 patients/year meet criteria). Recruitment will follow a standardized protocol developed specifically for the MGH Orthopedics Department consistent with prior recommendations, and informed by our prior IRB-approved study (protocol #: 2020P000095). We anticipate that potential participants will be identified through daily screening of Epic admission reports by the trained RA. The RA will next notify the medical staff (medical assistant) who will alert the surgeons. The surgeon will introduce study to the potential participants at the end of the medical visit if time allows. If the surgeon does not have time to introduce the study or if additional follow up to discuss the study is needed, the RA will contact referrals via telephone to provide details and conduct a phone screen using an IRB-approved script. We will also distribute our flyer, after getting approval from site leadership, to orthopedic clinics within the larger MGB infrastructure (such as Brigham & Women's Orthopedic Trauma Department) to expand our recruitment and maximize the geographic diversity in our sample. We will not be approaching these participants in-person, but they could complete a self-reported survey for screening and will receive a call from a RA with more information. All forms of recruitment, including patient flyers, will be submitted for IRB approval prior to use.

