#### **5. Subject Enrollment**

A trained RA will contact all referrals via telephone. The research assistant will make 3 attempts to contact referred potential participants before discontinuing. During the screening call, the RA will provide study details to participants and assess eligibility. The RA will be available to answer any questions from potential participants. The RA will review the consent form with eligible participants who express interest and intent to participate in the study. All participants will sign a REDCap-integrated e-consent form prior to study procedures. Individuals who do not meet study criteria or are not interested in participating will be offered a resource sheet with relevant health and mental health information for patients with acute orthopedic musculoskeletal injuries who are at risk for chronic pain and disability. The RA will maintain a detailed and updated log of all screening attempts for study data reports (i.e., % participants eligible, approached, recruited, enrolled). The principal investigator will review all cases in weekly meetings.

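### Does the recruitment marker need a written definition of who counts as approached before its Go/No-Go result can be trusted?

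*Combined protocol and SAP*

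**What the plan says.** The feasibility table in Section 9 sets two levels for recruitment: acceptable at "> 70% approached participate" and excellent at "≥ 80% of approached participate". On size, the same section states: "The sample size of 10 is appropriate for early feasibility testing". It adds that missed benchmarks require revisions before an efficacy trial. Section 3 makes the feasibility markers the pilot's primary outcome.

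The route to enrolment is in Sections 4b and 5:

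- The research assistant first screens hospital admission reports. Then: "The surgeon will introduce study to the potential participants at the end of the medical visit if time allows". Otherwise the research assistant telephones.
- Section 5 says: "During the screening call, the RA will provide study details to participants and assess eligibility". It expects some people to fail at this step: "Individuals who do not meet study criteria or are not interested in participating will be offered a resource sheet".
- Referrals receive up to three contact attempts. Consent is reviewed only with people who are eligible and interested, and every participant signs an electronic consent form before study procedures.
- Flyers go to other orthopedic clinics in the network. Section 4b says that these respondents are not approached in person, but "they could complete a self-reported survey for screening and will receive a call from a RA with more information".
- The research assistant keeps a "log of all screening attempts for study data reports (i.e., % participants eligible, approached, recruited, enrolled"), and the principal investigator reviews all cases weekly.

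**The concern.** Neither document section says who is in the denominator. In the described workflow a person hears about the study before, or in the same call as, the full eligibility check. Pain catastrophizing and pain anxiety scores, litigation and recent mind-body practice can hardly be read off an admission report. If everyone contacted counts as approached, the marker is no longer a measure of willingness. It becomes the eligible share multiplied by uptake among eligible patients, and it could fail through screen failures alone.

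Flyer respondents raise the opposite worry. They select themselves, so counting them could lift the marker over the threshold while uptake among patients approached in clinic is poor.

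The markers are meant to be fixed in advance. A denominator that can be chosen after the log is seen would weaken that, and the next trial needs eligibility and uptake as separate planning figures.

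**Working it through.** **Inputs from the documents.** 10 participants; acceptable above 70% (strict); excellent at 80% or more (all Section 9). The plan states no recruitment rate, so there is no figure of its own to reproduce.

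**Step 1: room in the marker.** The result is 10/m, where m is the number approached.

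| m | 10/m | Result |
|---|---|---|
| 12 | 83.3% | Excellent |
| 13 | 76.9% | Acceptable |
| 14 | 71.4% | Acceptable |
| 15 | 66.7% | Missed |

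The strict reading therefore leaves room for four people who do not join, whatever the reason.

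**Step 2: the literal reading.** Let e be the eligible share of those contacted and u the uptake among eligible patients. The marker equals e × u, so passing requires u > 0.70/e. The values of e are assumptions, because the documents give none.

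- e = 0.9: u must exceed 0.70/0.9 = 77.8%
- e = 0.8: u must exceed 0.70/0.8 = 87.5%
- e = 0.7: u must exceed 100%, which is impossible

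**Step 3: same log, different readings (hypothetical counts).** Take 10 participants, 2 eligible refusers, 3 people found ineligible on the call and 2 referrals never reached.

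- Eligible and reached: 10/(10 + 2) = 83.3%
- All reached: 10/(10 + 2 + 3) = 66.7%
- All contacted or tried: 10/(10 + 2 + 3 + 2) = 58.8%

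**Step 4: how far the examples are driven by their inputs.** A more dramatic log has 20 contacted, 7 ineligible, 3 refusers and 10 enrolled. It gives 10/20 = 50% against 10/13 = 76.9%. Its ineligible share is 7/20 = 35%, beyond the 30% at which Step 2 already makes a pass impossible, so the literal miss is built in.

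The flyer example has 6 flyer enrolees and 4 of 8 eligible clinic patients. It scores (6 + 4)/(6 + 8) = 10/14 = 71.4% with clinic uptake of 4/8 = 50%. It assumes that every flyer respondent enrols. If flyer respondents are left out, the marker is simply 4/8 and the masking disappears.

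**Step 5: which reading the text supports.**

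| Text | Points to |
|---|---|
| Log order in Section 5: eligible, then approached, recruited, enrolled | Eligible patients in the denominator |
| Admission reports screened before any contact (4b) | Eligible patients, as a first pass |
| Consent reviewed only with eligible, interested people (5) | Offer to participate comes after eligibility |
| Flyer respondents not approached in person (4b) | Flyer respondents outside the marker, though the later call leaves some doubt |
| Eligibility assessed on the screening call (5) | Contact before full eligibility: the one item for the literal reading |

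**Step 6: what can be recovered afterwards.** The log covers all screening attempts and reports eligibility separately from approach and enrolment. Screen failures can therefore be split from refusals under either reading. Recruitment route is the only element not named among its contents.

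**The case for a change.** The strongest case for a change is that a Go/No-Go marker should not need interpretation. The log's word order is not a definition, it carries no denominators, and it sits beside a contact sequence that runs the other way. Referrals never reached after three attempts have no stated place. Writing one sentence would cost almost nothing. Sections 3 and 4b also join the two risk scores with *and* where Section 4a uses *or*, so the eligible share is itself unsettled.

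Much of this stands as description: the term is undefined, and small counts can straddle 70%. A defined denominator would be tidier. But the sentence would record what a sensible analyst would do anyway, and the log already holds the counts needed to show screen failures beside the marker. The mismatch between the two risk scores is a separate inconsistency, which a definition of approached would not cure.

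The one proposal that goes beyond wording is to base the decision on the clinic route alone. That is a trade-off, not a correction. Section 3 names the flyer as a means of recruitment, and Section 4b uses it to widen the sample geographically. In the flyer example only 4 of the 10 participants would then count towards the marker, which makes an already coarse proportion coarser. The treatment of unreached referrals does not settle itself either: adding 2 of them to 10/13 = 76.9% gives 10/15 = 66.7%, so a sensitivity figure would only raise the threshold question again.

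**Conclusion.** No change to the plan is called for. The marker omits a definition, and the surrounding text points to the sensible one: eligible patients who were offered the study, with refusers kept in, and participation meaning signed consent. The exposure is real but small in kind. With 10 participants, three ineligible contacts could move 83.3% to 66.7%, but only under the less natural reading and on assumed counts. No screen-failure, refusal or flyer-uptake rate in the documents shows that this is likely.

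The consequence is also limited. This is one of nine descriptive markers in a single-arm pilot with no efficacy test, and a miss calls for revisions rather than ending the programme. A reader of the results who sees the log counts beside the percentage can tell a screening problem from a willingness problem. The conclusion rests on the log being kept as Section 5 describes and on its counts being reported with the marker. If only a bare percentage were published, the ambiguity would matter more.

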The skills-based VR will be self-administered by patients at-home over an 8-week period. The primary outcome for the pilot will be a-priori Go/No-Go feasibility markers (feasibility, acceptability, fidelity, credibility, expectancy, satisfaction) of the VR program and data collection procedures to increase the success of subsequent trials. To inform outcomes and mechanisms of action, we will integrate four quantitative assessment techniques: 1) multi-modal assessment (following IMMPACT criteria for pain trials) of pain intensity, pain-specific coping (catastrophizing, self-efficacy, acceptance), disability, physical function, and emotional function (depression, anxiety, stress); digital markers (VR use data, smartphone pain survey) for tracking dynamics of pain during the 8-week intervention; non-invasive fNIRS placed on the head (tissue blood perfusion and oxygenation) for brain activity during extremity movement and use of VR. Participants will travel to the clinic at baseline to pick up the VR equipment and complete the study assessments (self-reports and non-invasive fNIRS). Participants will return to the clinic after the 8-week intervention to repeat the assessment and drop off the VR. Given that skills-based VR has not been tested in this population, 30 min individual exit interviews will be critical for understanding patients' perception of: 1) the rationale and helpfulness of the skills; 2) the VR user experience; 3) barriers and facilitators to treatment adherence; 4) burden of the study procedures and data collection. The deliverables of this pilot study include: refined study protocol; preliminary feasibility; within-group signals of improvement; assessment of biomarkers; assessment of non-invasive fNIRS tissue perfusion and oxygenation; training in VR and mechanistic-based data collection; subsequent NIH proposal.

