## **6b. Intervention Period**

Enrolled participants that completed the baseline assessments will progress to the intervention period. Participants will receive the *RelieveVRx* program loaded in a Pico G2 4k head-mounted VR device at no cost. The Pico G2 4K device is commercially available, widely used, inexpensive, have minimal visual latency, and are easier for participants to use than many other devices (Figures 1 and 2). Importantly, the Pico G2 4k headset only records module completion and time. It does not collect or store biometric data on participants (e.g., eye tracking, breathing).

Figure 1. Participant view of *RelieveVRx* program.

Figure 2. Pico G2 4k head-mounted VR device and controller.

The package will also include a study welcome letter from the PI, patient-friendly instructions, a charger, and a pre-paid envelope to return the VR after the intervention period. Participants will be instructed to

self-administer 1 module of at-home VR (*RelieveVrx*) daily for 8 weeks. The RA will monitor participant completion of the device use in Curebase (modules completed, time worn) and daily logs (sent by Twilio) in REDCap. Curebase is a password-protected, HIPAA- compliant, online platform used in prior studies of *RelieveVrx*. The RA will contact participants to problem-solve barriers to VR use after 24 hours of non-wear.

The standardized 8-week VR program (*RelieveVrx*) delivers a multifaceted combination of pain relief skills training through a prescribed sequence of daily immersive experiences. The modules are informed by evidence-based principles of CBT, mindfulness, and pain neuroscience education. Each VR module is 2-16 minutes in length (average of 6 minutes). The VR treatment modules were designed to minimize triggers of emotional distress or cybersickness. Participants will complete the following *RelieveVrx* treatment modules:

- Pain education: visual and voice-guided lessons establish a medical and scientific rationale for the VR exercises and behavioral medicine skills for pain relief.
- Relaxation/Interoception: scenes that progressively change from busy/active to calm in order to train users to understand the benefits of progressive relaxation. User exhalation is measured by the microphone embedded in the Pico G2 hardware, offering biofeedback-enhanced relaxation exercises.

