- Mindful escapes: high-resolution 360 videos with therapeutic voiceovers, music, guided breathing, and sound effects designed to maximize the relaxation response and participant engagement.
- Pain distraction games: interactive games to train the skill of shifting focus away from pain.

Participants will receive text messages from Twilio, an MGH-approved smartphone app that our team has successfully used in similar R34 and U01 intervention development trials, to deliver daily study reminders and biweekly pain surveys (intensity and pain interference) during the intervention period. Participants will be informed of texting risks and provide consent for text messaging in writing or verbally if preferred. Participants will have the opportunity to ask questions about texting with study staff. Approval of text messaging and/or opting out of text messaging will be recorded in each participant's file. Participants may opt-out of the text message contact option at any point. This notification procedure was informed by prior orthopedic and pain participants in focus groups and exit interviews.

After the 8-week intervention period, the RA will contact participants again to schedule a return visit. The RA will repeat the assessment procedures for the self-reports and the non-invasive fNIRS. After completing the post-intervention assessments, participants will be invited to participate in individual exit interviews (30 min). The PI will conduct the exit interviews with an IRB-approved semi-structured interview script. If study participants are unable to schedule a 90-minute visit, post-tests and exit interviews may be conducted virtually at an alternate time. The purpose is to gather detailed feedback on intervention components, measures, procedures, and user experience with the VR.

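### Do the pain-survey and VR-attendance benchmarks in Section 9 need a written counting rule before they can be used?

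*Combined protocol and SAP*

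**What the plan says.** Section 3 gives the benchmarks their weight: "The primary outcome for the pilot will be a-priori Go/No-Go feasibility markers". Section 9 states the consequence: "If these benchmarks are not met, revisions will be necessary prior to an efficacy trial".

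Two of the nine rows in the Section 9 table are built from repeated records.

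- **Pain survey:** Acceptable is "> 70% of biweekly surveys"; Excellent has the same form at 80% or more. Section 6b describes the schedule only as "biweekly pain surveys (intensity and pain interference) during the intervention period", with no number and no days.
- **Treatment acceptability:** Acceptable is "> 70% attend 6 out of 8 weeks"; Excellent is 80% or more on the same criterion. Section 6b tells participants to "self-administer 1 module of at-home VR" each day for 8 weeks. Curebase records modules completed and time worn.

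For people who leave, Section 9 says: "Participants who drop-out will be counted as not meeting applicable feasibility criteria".

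**The concern.** A go/no-go marker fixed in advance should give one verdict for one set of data. On a first reading these two rows may not.

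The survey row takes surveys as its subject, whereas most of the percentage rows take people. Biweekly can mean every two weeks or twice a week. The drop-out sentence classifies people, which hints at scoring by person, but no personal completion cut-off is given. If surveys are pooled instead, nothing says what happens to those of someone who leaves.

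The attendance row borrows the language of weekly sessions, while this programme is a daily home exercise with no session to attend.

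At stake is whether two of the nine benchmarks count as met. If the counting rule were picked after the data were seen, it could be picked to suit the result.

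**Working it through.** The plan states no power, alpha or derived figure for these rows, so there is nothing to reproduce. The check applies the stated cut-offs (above 70%; 80% or more) to each reading.

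**Inputs.** N = 10, and cut-offs of 70% and 80% (Section 9); 8 weeks with one module daily, so 8 × 7 = 56 modules (Section 6b). Surveys per person are 4 or 16, the two readings of biweekly over 8 weeks. The personal survey cut-off (above 70%) and the modules needed per week (k) are assumptions; the documents give neither.

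**1. Thresholds**

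| Reading | Acceptable | Excellent |
|---|---|---|
| Pooled, 4 each | 29/40 = 72.5% | 32/40 = 80% |
| Pooled, 16 each | 113/160 = 70.6% | 128/160 = 80% |
| By person | 8/10 | 8/10 |

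By person, 7/10 is not above 70% and 8/10 already reaches 80%, so the two tiers coincide. Only pooling keeps them apart (29 to 31 of 40 is Acceptable but not Excellent).

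**2. Does 4 versus 16 flip a verdict?** Not by itself. Once surveys are sent, the number due is known. By person, the lowest count above 70% is 3/4 or 12/16, and both are 75%.

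**3. Pooled versus by person, same data (4 surveys each)**

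- Six answer all and four answer half: (6 × 4 + 4 × 2)/40 = 32/40 = 80%, Excellent; by person 6/10, not met.
- Eight answer 3 and two answer 1: (8 × 3 + 2 × 1)/40 = 26/40 = 65%, not met; by person 8/10, Excellent.

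**4. Drop-outs under pooling.** Two people leave at week 4 having answered both surveys due (4 in all). The other eight answer 27 of 32.

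- Surveys due until drop-out: (27 + 4)/(32 + 4) = 31/36 = 86%, Excellent.
- All scheduled surveys: 31/40 = 78%, Acceptable.
- Drop-outs set to zero: 27/40 = 68%, not met.

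**5. Attended week.** Six weeks need 6/56 = 11% of modules if k = 1, and 42/56 = 75% if k = 7. If everyone completes 3 modules every week (24/56 = 43%), 10/10 attend at k = 1 and 0/10 at k = 4. If everyone completes 5 (40/56 = 71%), 10/10 attend at k = 1, 4 or 5, and 0/10 at k = 7.

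**6. How often it matters, on assumed rates.** Ten people per trial, with each person's rate drawn from a beta distribution.

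- *Surveys* (40,000 trials): at mean completion 0.65–0.85 and between-person SD 0.1–0.3, pooled and by-person verdicts differ in about 12–27% of trials with 4 surveys and 13–65% with 16. At 0.90 (SD 0.1–0.2) and 0.95 (SD 0.1), they differ in about 1–13%.
- *Attendance* (20,000 trials): at mean daily use 0.60 (SD 0.1–0.2), the row is met with probability 1.00 at k = 1, about 0.10 at k = 4 and 0.00 at k = 5. At 0.90, it is 0.94–1.00 for k = 1 to 4, but only 0.02–0.39 at k = 7.

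**The case for a change.** The strongest case for a change is that these benchmarks are the primary outcome and carry the plan's only stated decision rule, so their counting rules should exist beforehand. The exact examples in steps 3 to 5 assume nothing about adherence rates, and the drop-out example spans all three verdicts. Being a pilot is no excuse, since a pilot exists to deliver these markers.

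Much of that stands: the definitions are absent and the flips are genuine. Three things limit its force.

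- **The text leans one way on surveys.** A percentage of surveys is most literally a pooled proportion. The drop-out sentence is confined to applicable criteria, so it need not turn this row into one about people.
- **A by-person rule has costs.** It would import a personal cut-off found nowhere in the documents and merge the two tiers at N = 10. It is also harder to meet: at 75% mean completion (SD 0.1–0.3), the pass probability is 0.42–0.46 by person against 0.65–0.71 pooled with 4 surveys, and 0.20–0.29 against 0.69–0.84 with 16.
- **The widest attendance contrasts need low use or an extreme k.** Section 6b provides daily reminders and a call from the research assistant after a day without wear. That makes one module a week an unlikely pattern, although the documents give no expected rate.

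**Conclusion.** No change to the plan follows. This is missing operational detail that analysts fill sensibly, not a rule that produces a wrong result. The number of surveys due is fixed once the messaging schedule runs. The survey row has a natural pooled reading that preserves both tiers. The attendance row has its unit, participants, and lacks only a weekly module count, which the investigators can set from the Curebase record. Writing these choices down would make scoring more transparent but would correct no error, and the one firm alternative, scoring surveys by person, is a debatable preference.

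The consequences are also bounded. Two of nine rows are touched, Section 9 disclaims any test of efficacy, and a missed row leads to revisions that the exit interviews inform as well.

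This rests on the choices being made without regard to the results, which the plan neither promises nor contradicts. It also rests on adherence not falling in the middle range, where readings diverge most (up to about 27% of simulated trials with 4 surveys and 65% with 16). If adherence does fall there, or the drop-out pattern in step 4 arises, these two verdicts should be read alongside the underlying counts.
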